## GLOSSARY OF ABBREVIATIONS

AE	Adverse Event
ASR	Annual Safety Report
BARS	Brief Adherence Rating Scale
BASEC	Business Administration System for Ethical Committees
ClinO	Ordinance on Clinical Trials in Human Research (in German: KlinV)
CRF	Case Report Form
CTCAE	Common Terminology Criteria for Adverse Events
DSM-IV	Diagnostic and Statistical Manual of Mental Disorders, Version 4
FADP	Federal Act on Data Protection (in German: DSGVO)
FOPH	Federal Office of Public Health
FPTM	Fragebogen zur Erfassung der Psychotherapiemotivation (in English: Questionnaire to measure the motivation for psychotherapy)
GCP	Good Clinical Practice
GSE	General Self-Efficacy Scale
G*Power	G*Power Statistical Power Analyses
HRA	Human Research Act
ICD-10	International Classification of Diseases, Version 10
ICH	International Conference on Harmonisation
MATRICS	Measurement and Treatment Research to Improve Cognition in Schizophrenia (Consensus Cognitive Battery)
MI	Motivational Interviewing
PANSS	Positive and Negative Symptom Scale
PUK	Psychiatrische Universitätsklinik Zürich (in English: Psychiatric University Hospital Zurich)
SAE	Serious Adverse Event
SNCTP	Swiss National Clinical Trial Portal
STAR	Scale to Assess Therapeutic Relationship
TAU	Treatment as usual

# 1 BACKGROUND AND RATIONALE

Psychosis includes perceptual and cognitive disturbances that are mediated, in most cases, by the dysregulation of dopamine and glutamate neurotransmission (Lieberman & First, 2018). The main symptoms of the disease have long been subdivided into positive and negative symptoms as well as cognitive deficits corresponding to clinical observations. Delusions, hallucinations, disorganized speech or behavior are described as the most common positive symptoms. Negative symptoms include a reduction or complete loss of motivation, interest, or expression (Stahl & Buckley, 2007).

Psychotic disorders are among the top ten causes of long-term disability (Murray & Lopez, 1996) and have a high chronicity potential and a high risk of invalidity (Kahn et al., 2015). Patients with psychosis are at risk for complications and derivative effects of psychosis, particularly suicide attempts, substance abuse, homelessness, victimization by others, and committing acts of violence (Lieberman & First, 2018). Especially schizophrenia, the most frequent form of psychotic disorders, is associated with a more severe course of illness and poorer outcomes compared to other psychotic and non-psychotic disorders (Jobe & Harrow, 2005). One-fifth of all patients with schizophrenia suffer from chronic symptoms and impairments (Owen et al., 2016), and the disease is associated with low long-term work performance (Rabinowitz et al., 2012), a high degree of all mental health care resources (Mueser & McGurk, 2004) and high socio-economic costs (Kennedy et al., 2014). These findings demonstrate the importance of sufficient treatment for psychotic disorders and, most importantly, point to a need for research so that more effective treatments can be developed in the future.

## *Psychotherapeutic interventions for psychosis*

In the recent decade, various psychotherapeutic programs with cognitive-behavioral background have been developed for patients with psychosis, and their efficacy has been investigated (Lincoln & Pedersen, 2019; Galderisi et al., 2021). Meta-analyses have shown superiority of cognitive-behavioral therapy for psychosis over standard treatment, both in combination with antipsychotic medication and without (Morrison et al., 2012, 2014). Many of the psychological approaches have focused primarily on treating the deficits associated with psychosis, as for example cognitive remediation or social skills training (Bark et al., 2003; Aghotor et al., 2010; Puig et al., 2014; Mehl & Lincoln, 2014). However, these methods are not feasible in the acute setting and there are only a few psychotherapeutic instruments that can be used within a short period of time for in-patient treatment.

The NICE-guidelines for the treatment of schizophrenia (National Institute for Health and Clinical Excellence, 2010) recommend a combination of antipsychotic medication and psychosis-specific cognitive behavioral therapy. This includes all stages of the illness, also in the acute phase (Kuipers et al., 2014). The Swiss Society for Psychiatry and Psychotherapy (SGPP) has stated in its treatment guidelines for schizophrenia that "our group recommends a structured psychotherapeutic approach even in the acute phase of the disease. The best evidence currently exists for cognitive-behavioral approaches, [...]. In any case, the psychotherapeutic procedure must be adapted to the circumstances of the acute phase and there is an urgent need for research on how this can be arranged in the setting of an acute ward." (Kaiser et al., 2016, p.10). Despite this explicit recommendation, to our knowledge there have been no studies that have systematically investigated this in the acute setting and results of which could therefore inform future treatment recommendations.

## *Rationale for planned project*

While recent guidelines for the treatment of psychotic disorders recommend to offer psychotherapy right from the start of the inpatient treatment, it is well known that psychotherapeutic interventions tend to be offered to patients relatively late in the course of the hospitalization – if at all. On the other hand, it has been shown that a majority of symptoms that patients with a psychotic disorder report as disturbing can be treated with psychotherapy (Freeman et al., 2019). The challenge is that there is little evidence on which mechanisms of psychotherapy are most

effective and applicable in the acute phase. As proposed by the SGPP, we would like to systematically test and evaluate psychotherapeutic interventions in the setting of an acute care unit in an initial pilot trial.

### *Expected relevance*

Therapeutic alliance during the acute phase of psychotic illness is one of the most pressing obstacles for successful long term recovery (e.g. Cavelti et al., 2016). In order for patients to accept much-needed medication and psychosocial therapy and not drop out prematurely, intrinsic motivation to adhere to therapy is crucial. Motivational Interviewing is a method, that has been developed and evaluated over the last three decades and that shows promising results, not only for patients with addiction but also for other patients who struggle with compliance and ambivalence towards treatment and change of behavior. For further information on the method see chapter 3.4. *Study intervention*.

At the same time, it is well known from clinical experience that patients are offered psychotherapy only late during the course of hospitalizations and not when it is most needed – during the acute phase of their illness. Accordingly, there is a clear gap in the literature as to which interventions are particularly useful in this challenging yet crucial phase of the illness.

We believe that the current project and the psychotherapeutic interventions tested here, can provide valuable data on acceptance, feasibility and effectiveness of such interventions and which can then be used to supplement a large multicentre trial across Switzerland.

## **2 STUDY OBJECTIVES AND DESIGN**

### **2.1 Hypothesis and Objectives**

The **primary objective** of the study is to investigate the impact of a brief intervention with Motivational Interviewing in an acute psychiatric inpatient setting on factors that impact treatment outcome such as therapeutic alliance and adherence to treatment.

The **second objective** is to examine if the effect of Motivational Interviewing can be measured in changes in symptom severity.

The **third objective** is to examine secondary effects of Motivational Interviewing on motivation for further psychotherapeutic treatment and higher expectations of self-efficacy after discharge from the hospital.

Therefore, the study grounds on three **hypotheses**:

1. Four sessions of psychotherapeutic intervention with motivational interviewing for newly admitted acute patients improves the therapeutic alliance and the adherence for treatment compared to supportive counseling.
2. Four sessions of psychotherapeutic intervention with motivational interviewing for newly admitted acute patients decreases symptom severity compared to supportive counseling.
3. Patients show higher motivation to seek psychotherapeutic treatment and have a higher self-efficacy expectation after leaving the inpatient stay, when they received an intervention with motivational interviewing compared to supportive counseling.

### **2.2 Primary and secondary endpoints**

Primary endpoints are the therapeutic alliance as assessed with the *Scale to Assess Therapeutic Relationship STAR* (McGuire-Snieckus et al., 2007) and adherence to treatment as measured with the *Brief Adherence Rating Scale BARS* (Byerly et al., 2008). These variables will be measured before and after the study intervention or control intervention.

Secondary endpoints include changes in symptom severity as assessed with the *Positive and*

*Negative Symptom Scale PANSS* (Kay et al., 1987), as well as the motivation for psychotherapy (measured with the German version of the *Questionnaire to measure the motivation for psychotherapy* by Schulz et al., 1995) and self-efficacy (measured with the *General Self-Efficacy Scale* by Schwarzer & Jerusalem, 1995). All secondary variables will be measured before and after the study intervention or control intervention.

As this study (risk category A) does not include drugs or other medical products and patients are hardly exposed to any more risks than in routine clinical care, no safety endpoints are defined.

## 2.3 Study design

This will be an interventional study with randomized control and open label trial. A parallel-group design with pre- and post-measurements (longitudinal design) will be employed, using subjective and objective measurements with questionnaires and structured interviews. It is a single center and national project.

The study consists of five phases:

1. Screening: Screening will be conducted by the applicant and master's students enrolled in the project who are bound to medical confidentiality, using electronic patient files at the hospital. The patients will be invited to the study by their treating physician or psychologist.

2. Pre-interventional measurement (1 session within the first week, max. 60minutes):

First, the psychopathological symptoms are to be assessed in order to decide about inclusion or exclusion (with PANSS; see also inclusion criteria). In addition, the therapeutic alliance and motivation for psychotherapy are measured. In order to record moderating effects or covariables, demographics (e.g. age, gender, education, years of illness) and two additional questionnaires will be added (attitude towards recovery and the individual motives).

3. Intervention (4 sessions within two weeks, 25- 40 minutes/session):

The patients receive either four sessions of motivational interviewing (intervention group) or four sessions of supportive counseling (control group). For Details see 2.4 "Study intervention"

4. Post-interventional measurement (1 session, max. 60 minutes): At the end of the intervention the motives, the negative symptoms, the hope for recovery, well-being and the level of functioning will be measured again.

The risk of bias should be kept at a minimum. Various precautions are being taken to this end.

- The most important confounding variables are controlled to prevent a bias.
- In order to avoid selection bias, patients are randomly assigned either to the intervention group or to the control group. Randomization is carried out at a 1:1 ratio, using pre-defined random lists (using the online randomization generator: <http://www.pub-med.de/tools/zufallsgenerator>) and a block schema prepared by the principal investigator.
- Block randomization ensures that the patients are distributed in the desired proportion to the two treatment modalities. All patients are randomized only once during the entire examination period.
- For minimizing bias some patients will have to be excluded from the study (see exclusion criteria)
- The study will be conducted as single-blind, as it is possible that the expectation towards one of the methods could have an impact on the outcomes.
- Raters will be blinded to the intervention and will receive prior training in the application of the rating scales.

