### 3.4 Withdrawal and discontinuation

Participants have the right to abort the study at any point and without providing a reason. The principal investigator and the co-investigator have the right to withdraw participants if they knowingly provide incorrect information, withdraw consent, do not adhere to protocol requirements (i.e. missing appointments, ignoring instructions) or if the disease has progressed (see exclusion criteria).

If participants do not finish the experiment, the data will be stored properly and taken into analysis as far as possible and useful. Additional participants will be recruited to replace the withdrawn participants.

Since they are inpatients, there is a very low risk of missed appointments. If this is still the case, the appointments can be made up on the following day.

If participants are discharged before the end of the study, they may attend the remaining appointments as outpatients if the majority of the study has already taken place (at least 3 psychotherapy sessions must have taken place during inpatient treatment).

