#### 4.2. Handling of missing data and drop-outs

All patients who completed the study will be taken into analysis. All collected data will be checked at each study assessment, and missing data will thus be avoided as much as possible. If missing data nevertheless does occur, data has to be excluded.

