## 8 MONITORING AND REGISTRATION

Monitoring visits at the investigator's site at the start and during the course of the study will help to follow up the progress of the clinical study, to assure utmost accuracy of the data and to detect possible errors at an early time point. The Sponsor-Investigator organizes professional independent monitoring for the study and will therefore collaborate with other research groups from the Psychiatric University Hospital.

All original data including all patient files, progress notes and copies of laboratory and medical test results will be available for monitoring. The monitor will review all or a part of the CRF and written informed consents. The accuracy of the data will be verified by reviewing the above referenced documents.

The monitoring plan for this study includes:

pre-study visit	-
Initiation / first visit	January 2023
Visits	One visit during the study intervention phase in April 2023
Review of key data	
 
• Existence and consent in 100% of patients
 
• 100% of the other key data (if available at the time of the visit) in at least 20% of the patients
 
• One 100%-source data comparison is performed for one patient
 

	from the sample
Additional contacts	Additional contacts by phone and/or e-mail will be made as required.
Final visit	August 2023

The study will be registered in the Swiss National Clinical Trial Portal (SNCTP via BASEC) and clinicaltrial.gov.

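### No allocation concealment is described: the principal investigator prepares the block schema, and Table 2 randomises before eligibility is checked

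*Combined protocol and SAP*

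**What the plan says.** **Allocation.** Section 2.3, under the aim of avoiding selection bias: "Randomization is carried out at a 1:1 ratio, using pre-defined random lists", made with an online generator, together with "a block schema prepared by the principal investigator". Block size is not given, nor whether it is fixed or varied.

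**Order of events.** Table 2 (Section 3.3) marks randomisation at visit 1 (day -3, plus or minus 2). The check of inclusion and exclusion criteria is at visit 2 (day 0), together with PANSS and the cognitive tests. Section 2.3 confirms that the PANSS at this pre-measurement feeds into the inclusion decision.

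**Who enrols.** The applicant and master's students screen, and treating physicians or psychologists invite (Section 2.3). The study coordinator and other hospital clinicians recruit (Section 3.2). The coordinator assigns participant numbers (Section 7.3).

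**Blinding.** It is stated for raters (Section 2.3) and patients (Sections 2.3 and 3.3) only.

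**Withdrawal.** Section 3.4: "The principal investigator and the co-investigator have the right to withdraw participants". The grounds include that they "do not adhere to protocol requirements (i.e. missing appointments, ignoring instructions) or if the disease has progressed". It adds: "Additional participants will be recruited to replace the withdrawn participants".

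**Analysis set.** Section 4.2: "All patients who completed the study will be taken into analysis" and "If missing data nevertheless does occur, data has to be excluded".

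**The concern.** Randomisation prevents selection bias only if the people who decide on entry cannot know the next allocation. Here the schema is prepared inside the study team by a named decision-maker, no barrier between the list and the recruiters is written down, and eligibility is settled after allocation. A borderline eligibility call could then go differently by arm without anyone intending it.

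At stake is whether the arms are comparable at entry. The baseline covariates in the ANCOVA (Section 4.1) adjust for measured baseline values only, not for unmeasured prognosis. In Table 2 the pre-measurement itself also follows randomisation, so these covariates are collected when the allocation already exists.

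**Working it through.** **1. The plan's own figure.** Section 4.1 gives f = 0.25, 80% power, alpha 0.05 and 64 per group. The noncentrality is N × f² = 128 × 0.0625 = 8. The noncentral F distribution with 1 numerator degree of freedom gives power 0.801, with or without one covariate. The 128 reproduces and is not disputed. For two groups d = 2f = 0.5, used below as a yardstick.

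**2. Order of events.** Randomisation is at day -3 and the eligibility check at day 0. Every exclusion made at visit 2 is therefore an exclusion of a patient already randomised.

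**3. Barriers between list and decision.** I looked for an independent list holder, sealed envelopes, central release, undisclosed or varied block size, and blinding of the principal investigator. None is described.

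**4. Predictability without the list (illustration).** Assume fixed blocks of size b = 2m, and an observer who knows b and all past allocations.
- Share fully determined = 1/(m + 1).
- Share guessed correctly = [m + ½(4^m / C(2m, m) − 1)] / (2m).
- For b = 4: 1/3 = 33%, about 43 of 128; and [2 + ½(16/6 − 1)]/4 = 2.833/4 = 71%.

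| Assumed block size | Fully determined | Guessed correctly |
|---|---|---|
| 2 | 50% | 75% |
| 4 | 33% | 71% |
| 6 | 25% | 68% |
| 8 | 20% | 67% |

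Enumeration of all balanced blocks gives the same values. Someone holding the list would know 100%.

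**5. From guessing to bias (illustration).** Suppose each guess moves the prognosis of the patient enrolled by +γ or −γ SD according to the arm expected. With c the share guessed correctly, bias = 2γ(2c − 1).
- b = 4: γ = 0.1 gives 0.2 × 0.417 = 0.083 SD; γ = 0.2 gives 0.167 SD.
- b = 8: 0.066 and 0.133 SD.

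If 0.1 to 0.2 SD is read as the whole contrast between the two kinds of patient, these values halve, to about 0.03 to 0.08 SD. The documents give no source for γ.

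**6. Withdrawal, a different route (illustration).** Simulation with no true effect, 64 per arm and an unadjusted t-test, 20,000 trials per setting. The least promising patients in one arm are replaced by unselected ones; r is the correlation between what the withdrawer sees and the outcome.
- 3 replaced, r = 0.3: bias 0.03 SD, two-sided type I error 5.5%.
- 6 replaced, r = 1.0 (an upper bound): bias 0.16 SD, type I error 18%.

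This route needs knowledge of the patient's current arm, not of the next allocation.

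**The case against.** A reader might infer that the principal investigator knows the upcoming allocations and uses them to decide who stays in the trial. The documents do not support that. Upcoming allocations bear on whom to enrol; they do not help anyone decide about a patient already randomised. Nothing says that the principal investigator enrols patients or consults the list during recruitment. Withdrawal is not free either: grounds are listed, and only non-adherence and disease progression leave much room for judgement.

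A reader might also infer that the plan uses fixed, guessable blocks. It mentions only a block schema. The percentages above concern someone without the list who knows the block size and has tracked every allocation. Therapists know the arm they deliver, but nothing says that they recruit study patients.

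Finally, concealing the list does not stop anyone learning a current arm from the therapists in a trial that Section 2.3 also calls open label. Concealment therefore cannot cure bias through withdrawal.

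All of this stands. It limits the claim to knowable, not known, and removes any firm figure for bias. It does not supply the missing concealment or change the order in Table 2.

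**Conclusion.** The point holds as a gap in allocation concealment. A member of the team with withdrawal rights prepares the schema, no concealment is described, and Table 2 randomises before eligibility is checked. The aim stated in Section 2.3 is therefore not secured.

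The size is not established. The 33% and 71% assume fixed blocks of four and a fully informed observer. The bias of 0.07 to 0.17 SD (13% to 33% of d = 0.5), or half of that on the narrower reading of γ, further assumes that every enrolment is steered. These figures show what could happen under such assumptions; they do not estimate what will. No misconduct is suggested. The change should be made because it is cheap and the defect cannot be repaired after enrolment.

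**What to change.** **Section 2.3.** Replace "a block schema prepared by the principal investigator" with a list generated by a named role at the hospital that has no part in enrolment, withdrawal, treatment or rating. Use randomly varied block sizes that are not disclosed to the team, and sequentially numbered, opaque, sealed envelopes. One possible source is the monitoring arrangement in Section 8, where the sponsor-investigator "will therefore collaborate with other research groups from the Psychiatric University Hospital". That is a planned collaboration, not an existing allocation service, so the task would have to be agreed. Envelopes avoid the need for that person to be available for each patient.

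**Table 2.** Move randomisation from visit 1 to after consent, the eligibility check and baseline measurement at visit 2, and open each envelope only then. The first session is at day 2, plus or minus 1, which leaves at least one day.

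**Sections 3.4 and 4.2, separately.** The steps above close the enrolment route only. For withdrawal and replacement, analyse all randomised patients as randomised wherever outcome data exist, and do not treat additional recruits as substitutes for withdrawn patients.

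**Cost.** A few hours of preparation and a small change in the visit schedule. If concealment already exists in practice, most of the Section 2.3 change is a matter of writing it down.

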## 2.4. Study intervention

Motivational interviewing (MI) is an intervention that helps people identify problems as such, build and maintain a commitment to change specific behaviors, and actually do so (Miller & Rollnick, 2002). It combines elements of behavior analysis with the principles of client-centered therapy, in which the patient learns to talk about his or her problems in empathetic but strategic

conversations. The therapeutic alliance plays a central role in this process. Ambivalence is not seen as resistance, but is respected and explored as a natural phenomenon, in order to support the patient's individual decision regarding the pros and cons. MI includes several techniques to help to manage ambivalence and decision making. If necessary, the patient is made aware of the ambivalences he or she has toward a specific topic (Barkhof et al., 2006).

In psychosis patients, there are several risk behaviors for relapse described in the literature, with the biggest problem of non-adherence to antipsychotic medication (Kane et al., 2013) which is consistent with our experience in clinical practice. The goal here is to guide patients to identify and increase their own motivation to change their behavior, and ultimately to ensure that psychiatric treatment is and remains effective. Accordingly, the overall goal of the intervention is to enter into a therapeutic alliance with the patient so that the patient's inner motivation to participate in treatment can be increased and the process can begin from within rather than being imposed from without.

Clinician-delivered motivational interviewing has been identified as effective for enhancing adherence among patients with psychosis (Kemp et al., 1996; Chien et al., 2016). Nevertheless, the literature also points to a lack of evidence. Although previous studies have shown that MI can positively influence important aspects of disease-related impairments, such as medication adherence, frequency and severity of psychotic relapses, duration of hospitalization, functional level, insight into the disease, and cognitive rehabilitation, data are still insufficient in schizophrenic patients (Reimer et al., 2019).

In our **study intervention**, patients should receive four sessions of motivational interviewing within two weeks. Throughout the MI sessions, interviewers use common MI techniques including open-ended questions, affirmations, reflections, summaries, asking permission, expressing empathy, supporting self-efficacy, etc. Interviewers are clinical psychologists who received MI training immediately prior to the study.

In the **control intervention** patients should also be given four sessions, in which no MI techniques take place. They will be carried out in the sense of supportive conversations. Supportive conversations aim to promote stabilization of the patient's current state without pursuing a goal set by the therapist. Supportive therapy includes tasks such as assistance with everyday requirements, emotional relief in the event of problems, or the provision of a reliable relationship. The topics are preferably defined by the patient. The clarification and processing of conflicts and problems that underlie the psychopathology is not usually the subject of therapy (Weierstall & Schonauer, 2016).

Since we want to check whether the patients really benefit from the specific intervention and not from getting more speaking time, the patient in the control group will also be given four conversations. It is known that supportive conversations can have a certain effect on the well-being and recovery process of patients, as the therapeutic relationship, i.e. appreciation, attention and/or attention, is an important efficacy factor (e. g. Grawe, 1995).

